6.2.4. Visit Windows

All data will be organized and analyzed according to the scheduled times as outlined in the protocol and by the visit denoted on the electronic case report form (eCRF) except for early termination (ET) visits during the treatment period.

If a subject terminates early and within the 26-week treatment period, the ET visit will be remapped based on the study day of the visit as follows.

ET Day Criteria	Visit
$1 \leq \text{study day} \leq 10$	Week 1
$11 \leq \text{study day} \leq 17$	Week 2
$18 \leq \text{study day} \leq 31$	Week 4
$32 \leq \text{study day} \leq 45$	Week 6
$46 \leq \text{study day} \leq 73$	Week 10
$74 \leq \text{study day} \leq 101$	Week 14
$102 \leq \text{study day} \leq 129$	Week 18
$130 \leq \text{study day} \leq 157$	Week 22
$158 \leq \text{study day}$, but not more than 3 days after treatment termination	Week 26

If a subject already has a scheduled visit at the mapped visit time, then the ET visit will be assigned as unscheduled at that mapped study week. If more than 1 observation is collected at a scheduled visit after baseline, the earliest value (based on collection or visit date) will be used at the visit, and other value(s) will be set as unscheduled. If the early termination visit date is more than 3 days after the date of last dose, then the visit will be assigned as unscheduled if EOS is available, or the visit will be assigned as EOS if EOS is missing.

These ET visit remapping rules will apply to all data points. All tables and figures will be presented by the remapped visit. All data listings will be reported using the visit as denoted on the eCRF.

6.2.5. Pooling of Centers

There will be no statistical analyses of endpoints by pooled centers in this study.

7. SUBJECT DISPOSITION

Subject disposition will be summarized for the enrolled population. Subjects who took at least one dose of study medication will be summarized by DB treatment and overall.

Subjects who completed the study and discontinued early from the study will be summarized by DB treatment and overall. The summary of subject disposition by discontinuation reason will be presented. If there are multiple reasons for discontinuation, the primary reason (determined by the investigator) will be used for the summary. All percentages will be based on the number of enrolled subjects within each DB treatment group and overall.

Using the safety population (defined in [Section 8.2](#)), the number of days until treatment discontinuation will be analyzed using Kaplan-Meier (KM) methodology. Subjects who complete the study treatment period will be censored on the study day of the last dose. Median, 25th percentile, and 75th percentile for days until discontinuation will be presented for each DB treatment and overall. A Kaplan-Meier plot will be used to display these results.

A listing of study completion will be provided for all enrolled subjects, with flags provided to identify subjects in the safety and ITT populations.

8. ANALYSIS POPULATIONS

8.1. ENROLLED POPULATION

The Enrolled population includes all subjects with an informed consent. All disposition summaries will be performed in the enrolled population.

8.2. SAFETY POPULATION

The Safety population includes all subjects who enter this study and receive at least one dose of study drug. All safety analyses will be performed in the Safety population.

8.3. INTENT-TO-TREAT (ITT) POPULATION

The ITT population is defined as all subjects who enter this study and receive at least one dose of study drug, and have a baseline effectiveness measure and at least one post baseline effectiveness measure in ADHD-RS-IV HV. The ITT population will be used for the effectiveness and quality of life analyses.

For the definition of ITT, the baseline effectiveness measure for determination of inclusion in the population is the OL baseline value.

9. PROTOCOL DEVIATIONS

Protocol deviations will be collected during monitoring visits. These deviations will be placed into the following categories: concomitant medications, dosing, enrolment criteria, laboratory, non-compliance, visit schedule, visit/procedure requirement, and other.

A summary table will be provided as the number and percentage of subjects with at least one important protocol deviation and the number of subjects in each category. A listing will be provided containing all protocol deviations.

10. DEMOGRAPHICS AND OTHER BASELINE CHARACTERISTICS

10.1. DEMOGRAPHICS AND OTHER BASELINE CHARACTERISTICS

Demographics (collected at enrollment into the SEP360-202 study) (sex, race, ethnicity, age [years], age group [6-9 and 10-12 years], weight [kg], height [cm], body mass index [BMI, kg/m²], and World Health Organization (WHO) z-scores and percentiles for height and BMI) will be summarized by DB treatment and overall for the safety and ITT populations. These values will be referred to as DB baseline values.

The age, age group [6-9 and 10-13 years], weight, height, BMI, and WHO percentiles for height and BMI at the time of enrollment into the SEP360-310 study will be summarized by DB treatment and overall for the safety and ITT populations. These values will be referred to as OL baseline values. Note that some subjects who were 12 years old at entry into SEP360-202 had turned 13 years old at the time of entry into SEP360-310.

Sex, race, age group, and ethnicity will be summarized by using summary statistics for categorical variables (frequencies and percentages). Percentages for sex, race, age group, and ethnicity will be based on the number of subjects within a DB treatment group. The DB baseline and OL baseline values for Age, height, height percentile, weight, BMI, and BMI percentile will be summarized by using summary statistics for continuous variables (number of subjects, arithmetic mean, standard deviation, 95% confidence interval for mean, median, minimum and maximum values).

Age will be calculated as the number of years between date of birth and date of enrollment into the SEP360-202 and SEP360-310 studies.

$$\text{BMI (kg/m}^2\text{)} = \text{Weight(kg)} / (\text{Height(m)})^2$$

Normal age and sex-based percentiles for weight, height, and BMI will be determined using the WHO growth charts.

BMI category: Underweight (< 5 percentile), Normal (≥ 5 - < 85 percentile), Overweight (≥ 85 - < 95 percentile), Obese (≥ 95 percentile).

A listing of demographic data will be provided for the enrolled population.

10.2. HISTORY

10.2.1. Medical History

In SEP360-202, medical history was coded using the Medical Dictionary for Regulatory Activities (MedDRA version 18.0). For subjects who enrolled in SEP360-310, the medical history data collected during the SEP360-202 study will be carried over into the SEP360-310 study database. The count and percentage of subjects under each history term, coded by system organ class (SOC) and preferred term (PT), will be summarized by DB treatment and overall. Percentages will be based on number of safety subjects within DB treatment group. Additionally, if a subject had 1 or more history events under any given SOC or PT, the subject will be counted only once under that SOC or PT.

A listing of medical history will be provided for the enrolled population.

10.2.2. Psychiatric History

Psychiatric history will be summarized by DSM-5. The psychiatric history data collected during the SEP360-202 study will be carried over into the SEP360-310 study database. The count and percentage of subjects under each DSM-5 code will be summarized by DB treatment and overall. All percentages will be based on the number of safety subjects within a DB treatment group. If a subject had 1 or more history events more than once, the subject will be counted only once under any given DSM-5 code.

A listing of psychiatric history will be provided for the enrolled population.

10.3. PRIOR AND CONCOMITANT MEDICATIONS

All medications will be coded using the World Health Organization drug dictionary (WHODRUG) version Quarter 1 2016 (March 1st, 2016). Medications ongoing at the time of completion of the SEP360-202 study will be carried over into the SEP360-310 study database.

The prior medications will include medications started prior to the first dose date of open-label study drug. The concomitant medications will include medications used on or after the first dose date of open-label study drug. Concomitant medications will include prior medications that continued use on or after the first dose of open-label study drug.

Concomitant medications will be separated into the following subsets:

- Medications used during the treatment period excluding medications that started on or after the last dose of open-label study drug
- Medications with start date on or after the first dose date of open-label study drug; this subset may include medications that had a change in dosage or frequency of use that had been used prior to open-label treatment.
- Medications started on or after the last dose of open-label study drug

For the summary tables, the count and percentage of subjects under each anatomical therapeutic chemical (ATC) class level 2 and PT will be summarized by DB treatment and overall. If a subject has taken 1 or more prior or concomitant medications more than once, the subject will be counted only once under any given drug class.

A listing of prior and concomitant medications will be provided for the enrolled population. Flags will be included in the listing to distinguish prior versus concomitant medications and to identify medications started on or after the last dose of open-label study drug.

10.4. TREATMENT EXPOSURE AND COMPLIANCE

Each subject will be dispensed one to three 10-day blister card(s) per scheduled visit based on his or her next expected visit date. Subjects will take 1 capsule of study medication per day at approximately the same time each morning. The number of capsules dispensed, the number of capsules returned, along with corresponding dates will be captured on the CRF and used to calculate exposure and compliance to study medication in terms of the number of doses taken.

First dose date in the SEP360-310 study will be based on the date of intake on the Dosing Accountability record. If the date of intake is missing on this record, it will be assumed the subject initiated one day after the first dispensation of SEP360-310 medication.

The last dose date will be based on the investigator's provided date on the disposition page. If the last dose date on the disposition page is missing, then last dose date will be based on the last date of intake from the Dosing Accountability log form that corresponds to the last dispensation of study drug.

Duration of Exposure (days) = Last dose date - first dose date + 1.

If a subject has only the first dose date and missing last dose date, the duration of exposure will be counted as 1 day.

If the subject has drug dispensed, but the first dose date is missing and the last dose date is missing, the duration of exposure will be counted as 1 day.

The duration of exposure to SEP360-310 study drug (number and percentage of subjects with exposure to study drug ≥ 1 day, ≥ 7 days, ≥ 14 days, ≥ 21 days, ≥ 28 days, ≥ 42 days, ≥ 56 days, ≥ 70 days, ≥ 84 days, ≥ 98 days, ≥ 112 days, ≥ 154 days, ≥ 168 days, ≥ 182 days) will be summarized by DB treatment and overall.

Cumulative exposure to dasotraline across the SEP360-202 and SEP360-310 studies will be summarized by DB treatment and overall. Cumulative exposure to dasotraline for a subject who received double-blind Placebo in the SEP360-202 study will be limited to the duration of treatment in the SEP360-310 study. Duration of treatment will be categorized as (≥ 1 day, ≥ 7 days, ≥ 14 days, ≥ 21 days, ≥ 28 days, ≥ 42 days, ≥ 56 days, ≥ 70 days, ≥ 84 days, ≥ 98 days, ≥ 112 days, ≥ 126 days, ≥ 140 days, ≥ 154 days, ≥ 168 days, ≥ 182 days, ≥ 196 days, ≥ 210 days, and ≥ 224 days).

Duration of SEP360-310 dose will also be provided by DB treatment group and overall. The number of days each dose was taken will be summarized.

The summary will also include the average daily dose (mg) for all subjects, the average daily dose (mg) for subjects who complete the study, the modal daily dose (mg) for all subjects, and the modal daily dose (mg) for subjects who complete the study. The modal daily dose will also be reported for each visit. The average daily dose is calculated as $[(2 \times \text{number of days 2 mg was taken}) + (4 \times \text{number of days 4 mg was taken}) + (6 \times \text{number of days 6 mg was taken})] / (\text{date of last dose} - \text{date of first dose} + 1)$. For each subject the modal daily dose is defined as the dose taken most frequently. Unscheduled visits will also be considered in the calculations when reporting data at each visit. If 2 or more different doses were taken an equal number of days, then modal

dose will equal the dose that the subject last takes. The number of days each dose was used will be summarized. Also, the total person-years during SEP360-310 will be summarized. The total person-years is defined as the sum of the duration of dosing in days for all subjects divided by 365.25.

A bar chart will summarize the percentage of subjects taking 2 mg, 4 mg, and 6 mg at each visit.

A summary will also be provided for the changes in dose from the previous visit. Categories that will be summarized include: maintained dose at 2 mg, down-titrated to 2 mg, up-titrated to 4 mg, maintained dose at 4 mg, down-titrated to 4 mg, up-titrated to 6 mg, maintained dose at 6 mg. Data from unscheduled visits will also be considered when assigning categories. The category will represent the change from the most recent visit. If the dose was changed during an unscheduled visit, then the category will represent the change from the most recent unscheduled visit.

Treatment compliance will be determined for each subject at each visit and over all visits. A descriptive summary will be provided.

Compliance = (Capsules Dispensed - Capsules Returned)*100/Capsules Expected. Subjects are expected to take 1 capsule per day. Only visits with both capsules dispensed and capsules returned will be included. For overall compliance if the number of capsules returned is missing for one or more visits for a subject, then overall compliance will be considered missing for that subject.

Subjects who take less than 75% of scheduled doses or who take more than 125% of scheduled doses will be considered noncompliant.

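### When both sources of the last dose date are blank, SAP 10.4 sets exposure to 1 day even if other records show longer dosing, so exposure is understated for those subjects

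*SAP*

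**What the plan says.** SAP section 10.4 sets out a short hierarchy. The first source is the disposition page: "The last dose date will be based on the investigator's provided date on the disposition page". If that is blank, "then last dose date will be based on the last date of intake from the Dosing Accountability log form", but only the entry "that corresponds to the last dispensation of study drug". Records for earlier dispensations are not named as a source.

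Duration is then "Duration of Exposure (days) = Last dose date - first dose date + 1". If no last dose date has been found, "If a subject has only the first dose date and missing last dose date, the duration of exposure will be counted as 1 day". Total person-years adds up these durations: "The total person-years is defined as the sum of the duration of dosing in days for all subjects divided by 365.25".

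The same section opens by saying that capsules dispensed and returned, with their dates, "will be captured on the CRF and used to calculate exposure and compliance to study medication in terms of the number of doses taken". The duration formula does not use them. The average daily dose in 10.4 is milligrams summed over the days at each dose, divided by the span from first to last dose date. It is written with the two dates and does not refer to the imputed duration.

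**The concern.** The 1-day rule applies whatever else is on file. Study drug accountability is scheduled at every clinic visit from 2E (Week 1) to 10E (Week 26) in Protocol Table 2, and Protocol section 10.7 has families bring unused drug to each visit for counting. A child seen through Week 22 and then lost has eight post-baseline accountability visits (2E to 9E), each at odds with a 1-day exposure. Protocol section 13.1 lists loss to follow-up among the expected reasons for termination. In that situation the record for the last dispensation could plausibly be blank, and it is the only log record the SAP consults.

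At stake is the description of long-term exposure in a study whose primary objective is long-term safety. The error runs one way. An affected subject drops out of every extension-study duration category from 7 days upward, adds almost nothing to person-years, and has cumulative exposure understated by the same number of days.

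**Working it through.** The plan gives no figure to reproduce here, so the check applies the SAP's own formulas.

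**Inputs from the documents**
- Planned enrolment: up to 330 (SAP 4.2).
- Full course: Day 1 to Day 182, so 182 − 1 + 1 = 182 days (Protocol 10.1; SAP 10.4 formula).
- Person-years: sum of days / 365.25 (SAP 10.4).
- Dose: 2 mg/day on Days 1 to 7, maximum 6 mg/day (Protocol 10.2).

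**Inputs assumed, because the documents do not give them**
- Number of subjects lacking a date in both sources.
- Their true exposure, and the mean exposure overall.

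**One subject.** Dosing up to the scheduled Week 6, 14 or 22 visit is 42, 98 or 154 days. The rule records 1, a loss of 41, 97 or 153 days.

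**Whole study, main illustration.** Assume a true mean of 130 days, and 5 to 17 affected subjects with 100 true days each.
- True total: 330 × 130 / 365.25 = 117.5 person-years.
- Loss with 5 affected: 5 × 99 / 365.25 = 1.36 person-years, and 1.36 / 117.5 = 1.2%.
- Loss with 17 affected: 17 × 99 / 365.25 = 4.61 person-years, and 4.61 / 117.5 = 3.9%.

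**Range under other assumptions.** Let all unaffected subjects complete 182 days.

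| Affected | True days each | True person-years | Under the rule | Loss |
|---|---|---|---|---|
| 3 (1%) | 42 | 163.29 | 162.95 | 0.2% |
| 3 (1%) | 154 | 164.21 | 162.95 | 0.8% |
| 10 (3%) | 42 | 160.60 | 159.48 | 0.7% |
| 10 (3%) | 154 | 163.67 | 159.48 | 2.6% |
| 16 (5%) | 42 | 158.30 | 156.51 | 1.1% |
| 16 (5%) | 154 | 163.21 | 156.51 | 4.1% |

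For the last row, the true total is (314 × 182 + 16 × 154) / 365.25 = 163.21 and the total under the rule is (314 × 182 + 16 × 1) / 365.25 = 156.51.

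**Average daily dose.** Take an assumed subject with 7 days at 2 mg and 147 days at 4 mg. The milligrams are 7 × 2 + 147 × 4 = 602, and with a proper last dose date the average is 602 / 154 = 3.91 mg/day. With no last dose date the SAP does not say what to do, and the programmer's choice decides the result:
- leave the denominator missing: the average is missing;
- put 1 in the denominator and keep all dosing days in the numerator: 602 mg/day;
- put 1 in the denominator and count only the first day's dose: 2 mg/day.

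**The case against.** The strongest reply is that this is a third-line rule with little reach. Accountability takes place at every treatment visit, and early terminators are asked back within 3 days (Protocol 13.1), so few subjects should lack both dates. The primary endpoint is adverse event incidence with Safety population counts as denominators (SAP 12.1). No exposure-adjusted rate and no inferential comparison is planned. The error understates long exposure, so it cannot make the safety database look larger than it is. The number of days at each dose is summarized separately. All of this stands and limits the consequence. It does not rescue a stated rule that returns a value the trial's own records contradict.

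A reader might infer more than the text supports, in three ways.
- *That a blank on the disposition page alone triggers the rule.* It does not; the accountability log for the last dispensation is tried first.
- *That the plan produces impossible average doses.* The rule imputes a duration, not a date, and the average-dose formula is written with dates. A value such as 602 mg/day needs two steps the SAP does not state: substituting the 1 day and keeping all dosing days in the numerator. What can be said is that the denominator is undefined.
- *That the 1 day carries into other analyses.* Last dose date is also used for carrying observations forward (SAP 6.2.3), early-termination remapping (6.2.4), time to discontinuation (7), concomitant medication subsets (10.3) and the split of on-treatment from post-treatment events (12.1). Since the rule creates no date, those uses are left without one; they are not set to Day 1.

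There is also a fair caution about the remedy. Taking the latest of several candidate dates, or treating unreturned capsules as swallowed, would bias exposure upward. Each weekly card holds 10 capsules for 7 days (Protocol 9.2.1), and SAP 10.4 itself sets overall compliance to missing when returns are missing. The fallback must allow for this.

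**Conclusion.** The concern holds for the exposure summaries. Once both date sources fail, SAP 10.4 assigns 1 day regardless of earlier accountability records or later visits. Duration categories, cumulative exposure and person-years are then biased downward for those subjects. This is a wrong stated rule, not just missing detail, and it sits badly with the section's own statement that capsule counts and dates are used to calculate exposure.

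The size is probably modest: 1.2% to 3.9% of person-years in the main illustration and 0.2% to 4.1% across the other scenarios. All these figures rest on assumed numbers of affected subjects and assumed true exposures. For the individual subject the error can be nearly the whole exposure. The average daily dose is undefined for these subjects, and nothing in the documents supports a claim that it will be impossible.

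**What to change.** Insert a further step in SAP 10.4 before the 1-day rule.

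1. If the last dose date is missing from both current sources, set it to the last documented intake date on any earlier accountability record.
2. If there is none, derive it as first dose date + capsules accounted for − 1. Capsules accounted for means dispensed minus returned, with unreturned cards not counted as taken. The date may be no later than the last visit with accountability.
3. Count exposure as 1 day only when there is no post-baseline evidence of dosing.
4. Use the same imputed date in the average-dose denominator and wherever else the SAP needs a last dose date.
5. Flag the imputed subjects and report their number by DB treatment group and overall.

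In the same edit, reconcile two overlapping rules. When the intake date is missing, "it will be assumed the subject initiated one day after the first dispensation of SEP360-310 medication", yet a later rule covers drug dispensed with both first and last dose dates missing. The SAP should say which takes precedence.

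The cost is SAP wording, a small amount of programming and a little imputation. The data are already on the CRF.

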11. EFFECTIVENESS ANALYSIS

11.1. CHANGE IN ADHD-RS-IV

The first effectiveness endpoint is the change from DB baseline and change from OL baseline in Attention Deficit Hyperactivity Disorder Rating Scale-fourth edition (ADHD RS-IV) HV total score. The primary study population is the ITT population.

The ADHD RS-IV HV includes 18 questions about frequency of recent symptoms of ADHD. ADHD RS-IV HV score is collected at each visit. Each question is scored on a 4-point scale ranging from 0 (no symptoms) to 3 (severe symptoms) with total score ranging from 0 to 54. The 9 odd-numbered items (i.e. 1, 3, 5, 7, 9, 11, 13, 15, and 17) assess inattentive symptoms, and the 9 even-numbered items (i.e. 2, 4, 6, 8, 10, 12, 14, 16, and 18) assess hyperactive-impulsive symptoms. Hence, for inattention subscale, the score is obtained by adding the responses to the scores of the 9 odd-numbered items, and for the hyperactivity-impulsivity subscale, the score is obtained by adding the scores of the 9 even-numbered items. The total score is obtained by adding the inattention and hyperactivity-impulsivity subscale scores.

The observed value, change from DB baseline, and change from OL baseline for the ADHD RS-IV total score will be summarized descriptively by DB treatment and overall, and by visit (Week 1, Week 2, Week 4, Week 6, Week 10, Week 14, Week 18, Week 22, Week 26, and Week 26 (LOCF)).

The line-plot of Mean (\pm SE) change from DB baseline in ADHD RS-IV HV total score will be provided by DB treatment and overall, and visit using the ITT population. At baseline, the change from baseline will be displayed as 0. A similar line-plot will be produced showing the change from OL baseline.

